### **1.4 Endpoints**

- 1.4.1 Primary: Complete response rate (CRR) at end of treatment restaging, by the revised International Working Group Criteria (see appendix A)
- 1.4.2 Secondary:
- Rate of grade III and IV adverse events or discontinuation due to toxicity
  - Overall response rate (ORR) at end of treatment restaging
- 1.4.3 Exploratory:
- Failure-free survival (FFS)
  - Overall survival (OS)

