## **2. BACKGROUND**

### **2.1 Study Agent(s)**

- 2.1.1 Brentuximab Vedotin (SGN-35, Adcetris)

Brentuximab vedotin is an anti-CD30 antibody-drug conjugate (ADC) consisting of an IgG1 antibody against CD30 bound to the anti-microtubule agent monomethyl auristatin E (MMAE). There have been two phase II studies of single agent brentuximab in relapsed/refractory cHL and relapsed/refractory systemic anaplastic large cell lymphoma (ALCL). In the pivotal phase II study of cHL 102 patients received brentuximab at 1.8 mg/kg every 3 weeks. This patient population was heavily pre-treated with a median of 3.5 prior treatments. Seventy-five percent of patients had an objective response (complete or partial remission) with median duration of approximately 9 months. Thirty-four percent of patients achieved a complete response (CR). In the phase II study of relapsed or refractory ALCL 38 patients received brentuximab also at 1.8 mg/kg every 3 weeks. Seventy-two percent of patients were ALK negative (which typically carries a poor prognosis) and patients had received a median of 2 prior systemic therapies. The objective response rate (ORR) was 86% with CR obtained in 53% of patients (median duration of response not yet reached). Nearly all patients (>90%) in both studies experienced a reduction in tumor volume. A phase I study evaluated the combination of brentuximab vedotin with either ABVD or AVD (without bleomycin). The bleomycin-containing arm was found to induce excess pulmonary toxicity, but brentuximab with AVD was found to be overall well tolerated with excellent efficacy in patients with advanced stage disease. The recommended phase II dose for brentuximab combined with AVD is 1.2 mg/kg every 2 weeks.

Brentuximab has been well tolerated in clinical trials to date (see section 6.1). Treatment-associated adverse events (AEs) occurring in  $\geq 20\%$  of patients in the phase II studies combined include peripheral sensory neuropathy (44%), fatigue (42%), nausea (41%), diarrhea (34%), pyrexia (31%), upper respiratory tract infection (28%), neutropenia (21%), and vomiting (20%). These events were primarily Grade 1 or 2, with the exception of neutropenia, for which Grade 3 and grade 4 events were reported for 13% and 7% of patients, respectively. Importantly, most of the peripheral sensory neuropathy events were reversible. Also, of note, similar patterns and incidences of AEs were generally observed for HL and ALCL patients.

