##### 13.1.1 Primary Endpoint and Sample Size

The primary endpoint of this study is complete response rate at EOT restaging. A one-stage design is used. A total of 34 participants will be entered on this study. The expected accrual is 1-2 participants per month. If at least 91% (31) of evaluable participants achieve complete responses, the treatment will be considered promising and worthy of further study. Patients removed from study prior to initial restaging for reasons other than disease progression are not considered evaluable for response. The study has 91% power and 0.09 one-sided type I error to test a CR rate of 95% vs. a CR rate of 81%. With 34 eligible patients the 90% confidence interval for the true response rate will be no wider than 30%. If greater than 2 evaluable participants are seen not to have disease response (CR or PR) following brentuximab-AD therapy, the study will stop. Assuming the null response rate of 81%, the study will stop early with a maximum probability of 0.97. Under the promising rate, the study will stop early with a maximum probability of 0.24.

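### Section 13.1.1: the stated 91% power and 0.09 type I error leave out the CR/PR stop, while the 0.97 and 0.24 stopping maxima count every non-CR as a non-responder, so the two pairs cannot both hold if the stop overrides success

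*Combined protocol and SAP*

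**What the plan says.** Everything at issue stands in one paragraph, section 13.1.1 (Primary Endpoint and Sample Size) of the combined protocol and SAP. The design is described as one-stage, with 34 participants and CR at end-of-treatment restaging as the primary endpoint.

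- Success rule: "If at least 91% (31) of evaluable participants achieve complete responses, the treatment will be considered promising and worthy of further study".
- Operating characteristics: 91% power and 0.09 one-sided type I error, for a CR rate of 95% against 81%.
- Stopping rule: "If greater than 2 evaluable participants are seen not to have disease response (CR or PR) following brentuximab-AD therapy, the study will stop".
- Stopping probabilities: "Assuming the null response rate of 81%, the study will stop early with a maximum probability of 0.97", and "Under the promising rate, the study will stop early with a maximum probability of 0.24".

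The success rule counts CRs. The stopping rule counts participants with neither CR nor PR, which is the complement of overall response, a separate secondary endpoint in section 1.4 ("Overall response rate (ORR) at end of treatment restaging"). No overall response rate is assumed for planning. Sections 13.1 to 13.1.4 do not say whether a stop rules out a positive conclusion, or whether power and alpha allow for it.

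**The concern.** Three non-CRs are compatible with success, but three non-responders trigger the stop. The rules collide in one final outcome: 31 CRs, three SD/PD and no PR. The stop is worded without conditions, so a team that follows it could halt a trial that can still reach 31 CRs. A team that sets it aside could face a dispute over its claim after the data are known.

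The quoted figures do not resolve this, because each pair answers a different question. Power and alpha describe the 31/34 rule with no stop in place. The stopping probabilities describe the stop when every non-CR is a non-responder. At stake are the power the trial really has and the reading of that one outcome. The false-positive rate is not at risk.

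**Working it through.** **Inputs.** From section 13.1.1: n = 34, success at 31 or more CRs, CR rates 95% and 81%, stop at three or more evaluable participants without CR or PR. All 34 are taken as evaluable. The documents give no share f of non-CRs that are SD/PD, so f is an assumption, varied from 0 to 1 and taken as equal at both CR rates.

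**1. Reproduce power and alpha.** Let N be the number of non-CRs, binomial with n = 34 and probability 1 − CR rate. Success is N ≤ 3.

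- CR 95%: P(N = 0, 1, 2, 3) = 0.1748, 0.3128, 0.2717, 0.1525; sum 0.912 (stated 91%).
- CR 81%: 0.0008, 0.0062, 0.0239, 0.0597; sum 0.091 (stated 0.09).

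The stop plays no part in either figure.

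**2. Reproduce the stopping maxima.** If no non-CR is a PR, P(stop) = P(N ≥ 3).

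- CR 81%: 1 − 0.0308 = 0.969 (stated 0.97).
- CR 95%: 1 − 0.7593 = 0.241 (stated 0.24).

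If only the first 33 participants could trigger the stop, the values would be 0.964 and 0.227. The stated figures therefore use all 34 and include the disputed outcome.

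**3. Compare the pairs.** If a stop excludes success, the two probabilities cannot sum to more than 1. At CR 95% they give 0.91 + 0.24 = 1.15; at CR 81%, 0.09 + 0.97 = 1.06. In the no-PR case behind the stopping figures, the overlap is P(N = 3): 0.153 and 0.060.

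**4. Include the stop.** A stop that overrides success removes only the outcome with N = 3 and all three SD/PD:

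P(success) = P(N ≤ 3) − P(N = 3) × f³

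P(stop) = P(Bin(34, f × (1 − CR rate)) ≥ 3)

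| f | Power (CR 95%) | Alpha (CR 81%) | P(stop), CR 95% | P(stop), CR 81% |
|---|---|---|---|---|
| 0 | 0.912 | 0.091 | 0 | 0 |
| 0.4 | 0.902 | 0.087 | 0.03 | 0.48 |
| 0.5 | 0.893 | 0.083 | 0.05 | 0.64 |
| 0.75 | 0.848 | 0.065 | 0.13 | 0.88 |
| 1 | 0.759 | 0.031 | 0.24 | 0.97 |

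For example, at f = 0.4: 0.9119 − 0.1525 × 0.064 = 0.9021.

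**5. Reference values for f in the documents.** These are single-agent results in relapsed disease, so a guide only. Section 2.1, Hodgkin lymphoma: 75% response and 34% CR give 25/66 = 0.38. Section 2.1, anaplastic large cell lymphoma: 86% and 53% give 14/47 = 0.30. Prescribing information, Table 3: 73% and 32% give 27/68 = 0.40. Power at these shares is 0.902 to 0.908, and alpha 0.087 to 0.089.

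**6. If the stop only halts accrual.** Suppose participants already enrolled are still counted towards 31 CRs, and L more have been enrolled by the time the third failure is known. Given exactly three failures in 34, all 34 are already in with probability 1 − C(33 − L, 3)/C(34, 3).

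End-of-treatment PET falls 6 weeks after the last dose. With 4 cycles that is 98 + 42 = 140 days from first dose (4.6 months); with 6 cycles, 154 + 42 = 196 days (6.4 months). At 1 to 2 participants a month, L is about 5 to 13. If failures show at the cycle 2 PET (about 49 to 55 days), L is about 2 to 4.

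Power with f = 1 is 0.7593 + 0.1525 × that probability:

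- L = 0: 0.773
- L = 2: 0.797
- L = 4: 0.819
- L = 5: 0.828
- L = 13: 0.883

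**The case against.** The strongest reply is that nothing in the paragraph is miscalculated. Each figure reproduces, and both stopping probabilities are labelled as maxima, a legitimate way to present a CR/PR stop when no PR rate is assumed. Power and alpha computed without a futility stop are coherent if the stop is non-binding, and the one-stage description fits that reading. All of this stands. What it leaves open is that the stop is worded without conditions and is nowhere called non-binding.

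The reply continues that an SD/PD share near 1 is unlikely. Appendix A classes reduced uptake with a Deauville score of 4 or 5 as a partial response, and section 2.1 reports tumour shrinkage in over 90% of relapsed patients. That also stands as an argument about size: on the shares that the documents offer, the loss is about one point at most.

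A reader might infer three stronger things:

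- **The 0.97 and 0.24 figures are wrong.** They are not; they are the exact upper bounds.
- **The trial's true power is 76%.** That value needs every non-CR to be SD/PD and the stop to veto success. The plan assumes neither.
- **The type I error is inflated.** It is not; including the stop can only lower it.

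**Conclusion.** The concern holds in a limited form. If the stop is followed as written and overrides success, 91% is the upper limit of power, reached only when no non-CR is SD/PD, whereas 0.24 applies only when all of them are. Both cannot describe the same trial.

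The size depends on a share that the documents do not give. Over the full range, power at CR 95% runs from 0.912 to 0.759 and alpha at CR 81% from 0.091 to 0.031. The power loss is about one point or less up to a share of about 0.4. If the stop only halts accrual, the all-SD/PD power is about 0.77 to 0.88, depending on assessment lag.

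These results assume 34 evaluable participants and the same SD/PD share at both CR rates. The point merits correction because the plan leaves one outcome with two opposite readings and does not say which rule its power and alpha describe.

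**What to change.** Reconcile the two rules in section 13.1.1 by stating which one governs when 31 CRs occur with three SD/PD, and whether a stop vetoes success or only halts accrual.

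- If the stop is binding, restate power and alpha as the range with the stop included. Under a veto that is 0.912 down to 0.759 and 0.091 down to 0.031.
- If it is non-binding, say that power and alpha are computed without it.

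It would help to note that 0.97 and 0.24 are the bounds when no non-CR is a PR. Stopping probabilities at chosen overall response rates are optional.

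The cost is two or three sentences. No participants are added, and neither the 31/34 criterion nor the stopping rule has to change; the choice of stopping rule stays with the sponsor.

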##### 13.1.2 Secondary and Exploratory Endpoints

Overall Survival (OS) will be measured from date of study entry to date of death and characterized using the Kaplan-Meier method. Failure-free Survival (FFS) will be measured from date of study entry to date of documentation of treatment failure and calculated using the Kaplan-Meier method. Treatment failure is defined as: progressive disease, failure to achieve a complete remission, or relapse after initial response. This study is not powered for FFS, but our hypothesis is that it will achieve a 2 year FFS of  $\geq 87\%$ , consistent with all prior studies of

chemotherapy alone in non-bulky limited stage HL. Two year FFS less than this will not be considered worthy of further investigation.

All participants who receive treatment, regardless of eligibility, will be assessed for toxicity.

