**Revised criteria for response assessment**

	PET-CT-based response
	Complete Metabolic Response (CMR)
Lymph nodes and extralymphatic sites	Score 1, 2, or 3 with or without a residual mass on 5-point (Deauville) scale (see below)  It is recognized that in Waldeyer's ring or extranodal sites with high physiological uptake or with activation within spleen or marrow, e.g. with chemotherapy or myeloid colony stimulating factors, uptake may be greater than normal mediastinum and/or liver. In this circumstance, CMR may be inferred if uptake at sites of initial involvement is no greater than surrounding normal tissue even if the tissue has high physiological uptake
Non-measured lesion	Not applicable
Organ enlargement	Not applicable
New lesions	None
Bone marrow	No evidence of FDG-avid disease in marrow
	Partial Metabolic Response (PMR)
Lymph nodes and extralymphatic sites	Score 4, 5 with reduced uptake compared with baseline and residual mass(es) of any size. At interim these findings suggest responding disease  At end of treatment these findings indicate residual disease
Non-measured lesions	Not applicable
Organ enlargement	Not applicable

CONFIDENTIAL

This document is confidential. Do not disclose or use except as authorized.

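### The only interim stop counts CR or PR rather than CR, so accrual can continue after 31 CRs of 34 are out of reach if at least two of the first four non-CRs are PRs

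*Combined protocol and SAP*

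**What the plan says.** Section 13.1.1 sets the endpoint ("The primary endpoint of this study is complete response rate at EOT restaging"), the design ("A one-stage design is used") and the size ("A total of 34 participants will be entered on this study"). The regimen is called promising on this condition: "If at least 91% (31) of evaluable participants achieve complete responses". The error rates given are 0.09 one-sided and 91% power, for a CR rate of 81% against 95%.

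The same section has one interim rule: "If greater than 2 evaluable participants are seen not to have disease response (CR or PR) following brentuximab-AD therapy, the study will stop". It puts the chance of stopping early at no more than 0.97 under the null rate and 0.24 under the promising rate.

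Two other places say how the plan regards a partial response at the end of treatment. Section 13.1.2, for failure-free survival: "Treatment failure is defined as: progressive disease, failure to achieve a complete remission, or relapse after initial response". Appendix A says of the PET findings that define a partial metabolic response that, at end of treatment, "these findings indicate residual disease".

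No section sets a stopping threshold on the number of CRs. Section 11.2 allows the DSMC to be given response information but attaches no efficacy limit to it.

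**The concern.** A PR counts for the regimen in the stopping rule and against it in the success rule. The stop therefore sees only those non-CRs that are stable disease, progression or otherwise no response. If the failures are mainly PRs, the trial can reach a point where the success criterion cannot be met and still be open to accrual.

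What is at stake is exposure. The participants are previously untreated, with limited-stage disease for which section 2.2 quotes cure rates above 85%. After that point, new patients start a regimen that the plan's own criterion can no longer call promising.

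**Working it through.** **Inputs.** From 13.1.1: N = 34, success at 31 or more CRs, CR rates 0.81 and 0.95, stop at 3 or more evaluable patients without CR or PR, accrual 1-2 per month. From sections 5 and 9.1: patients in PR or SD at interim receive 6 cycles, and the end-of-treatment PET is 6 weeks after therapy. The share f of non-CRs that are PRs is not in the documents, so it is varied from 0 to 1.

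**1. The plan's own figures (exact binomial, n = 34).**
- P(at least 31 CRs) = 0.0906 at 0.81 and 0.9119 at 0.95. The stated 0.09 and 91% are reproduced.
- P(at least 3 events) = 0.969 at event rate 0.19 and 0.241 at 0.05. The stated 0.97 and 0.24 are reproduced, but 0.19 and 0.05 are the non-CR rates (1 - 0.81 and 1 - 0.95). For a rule that counts CR or PR they are upper bounds, reached only if no non-CR is a PR. By true CR + PR rate, the rule stops with probability 0.90 at 85%, 0.67 at 90%, 0.24 at 95% and 0.08 at 97%.

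**2. When success becomes impossible.** 34 - 31 = 3 non-CRs are allowed, so the fourth rules out 31. P(at least 4 non-CRs of 34) = 0.909 at a CR rate of 81% and 0.088 at 95%.

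**3. When the existing stop misses this.** Of the first four non-CRs, the stop has fired if three or four are not PRs. It has not fired if at least two are PRs. The chance of finishing 34 patients with at least 4 non-CRs and no stop is the sum over k = 4 to 34 of P(k non-CRs) x P(at most 2 of the k are not PRs). At a CR rate of 81%:

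| PR share of non-CRs | Probability | Given at least 4 non-CRs |
|---|---|---|
| 0% | 0.00 | 0% |
| 25% | 0.05 | 6% |
| 50% | 0.28 | 31% |
| 75% | 0.69 | 76% |
| 100% | 0.91 | 100% |

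**4. Enrolments avoided.** The last dose of a six-cycle course falls 5 x 28 + 14 = 154 days after the first. Adding 42 days to the PET gives 196 days, or 6.4 months. Accrual was simulated with random (Poisson) entry, all 34 evaluable and every non-CR known 6.4 months after entry. The existing stop alone was compared with the existing stop plus a stop at the fourth non-CR. True CR rate 81%; the lower figure is for 2 patients per month, the upper for 1 per month:

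| PR share of non-CRs | Mean enrolments avoided |
|---|---|
| 0% | 0 |
| 25% | 0.7-1.1 |
| 50% | 2.1-4.1 |
| 75% | 3.7-7.2 |
| 100% | 4.0-8.4 |

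At a true CR rate of 95%, the added stop shortens accrual beyond the existing one in at most about 5% of trials. All of those would miss 31 anyway.

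**5. Effect on the test.** The added stop acts only when 31 can no longer be reached, so it turns no success into a failure and no failure into a success. The 0.0906 and 0.9119 do not move.

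**The case against.** The plan declares a one-stage design, and leaving out curtailment biases nothing. ORR is a named secondary endpoint (1.4.2), so a stop on CR or PR is a coherent guard against plain inactivity. The sponsor's preceding 34-patient trial preliminarily had every patient in CR after 2 cycles (2.1.1), so a fourth non-CR may never occur. Stopping is not free either: four end-of-treatment failures still leave 30/34 = 88.2%, above the 87% two-year FFS mark in 13.1.2, so that question would be open when accrual ended. All of this stands. It makes the point an inexpensive improvement and not an error in the test.

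A reader might infer three stronger things, and the documents support none of them:
- *That accrual always continues past the fourth non-CR.* SD and PD are non-CRs too, and three of them stop the study under the present rule.
- *That the all-PR saving is the expected one.* No PR share is given. A shorter lag of 4.6 months (four cycles) would raise the saving, but four cycles are for patients in CR at interim, so most end-of-treatment PRs will follow six. Progression seen at the cycle 2 PET could also fire the existing stop sooner than assumed here, which would shrink the saving.
- *That four is always the limit.* It holds for 34 evaluable. With 33, only 2 non-CRs are allowed: 30/33 = 90.9%, short of 91% taken strictly and of 31. With 32, the count of 31 allows 1 and the 91% allows 2 (30/32 = 93.8%, 29/32 = 90.6%).

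**Conclusion.** The point holds in a conditional form. The plan's only interim stop does not monitor its primary endpoint. With 34 evaluable, accrual can run on after success is impossible whenever at least two of the first four non-CRs are PRs.

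At a true CR rate of 81%, the mean cost is between 0 and about 8 enrolments out of 34. Where it falls in that range depends on the unknown PR share and on accrual speed, under the assumed 6.4-month lag. At a true CR rate of 95% the gap hardly matters. The final test keeps its stated type I error and power with or without the change. It should be fixed because the fix is cheap and the plan already accepts an early stop on response.

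**What to change.** Add to 13.1.1: *Accrual will also stop once the number of evaluable participants without a CR at end of treatment (PR, SD, PD, early death or not assessable) means the success criterion can no longer be met (4 when 34 are evaluable; fewer if fewer are evaluable).* State whether the count of 31 or the 91% governs when fewer than 34 are evaluable. Leave the 31/34 cut, the 91% power and the 0.09 type I error as they are.

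In the same edit, confirm whether the existing stop is meant for CR or for CR plus PR, and at which assessment non-response is counted. If CR plus PR is meant, give its stopping probabilities under assumed CR + PR rates and say that 0.97 and 0.24 are upper bounds. If CR is meant, the existing stop would fire at the third non-CR, while 31 of 34 is still reachable. The added sentence would then not be needed for 34 evaluable, but the stop and the success rule would have to be reconciled.

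The cost is a few lines of text; the response data are already collected. If the added stop fires, fewer patients inform safety, ORR and the two-year FFS criterion, so those already enrolled should still be followed for all three.

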##### 13.1.2 Secondary and Exploratory Endpoints

Overall Survival (OS) will be measured from date of study entry to date of death and characterized using the Kaplan-Meier method. Failure-free Survival (FFS) will be measured from date of study entry to date of documentation of treatment failure and calculated using the Kaplan-Meier method. Treatment failure is defined as: progressive disease, failure to achieve a complete remission, or relapse after initial response. This study is not powered for FFS, but our hypothesis is that it will achieve a 2 year FFS of  $\geq 87\%$ , consistent with all prior studies of

chemotherapy alone in non-bulky limited stage HL. Two year FFS less than this will not be considered worthy of further investigation.

All participants who receive treatment, regardless of eligibility, will be assessed for toxicity.

#### 13.1.3 Evaluation of toxicity

All participants will be evaluable for toxicity from the time of their first treatment. Participants will be assessed for toxicity with each treatment and participants with unacceptable toxicity will be removed from the study. All participants who receive treatment, regardless of eligibility, will be evaluated for toxicity.

#### 13.1.4 Evaluation of response

All participants who reach initial restaging scan will be evaluable for response, as will subjects who are removed from study prior to initial restaging due to clinical disease progression. Patients removed from study prior to initial restaging for reasons other than disease progression are not considered evaluable for response. Each participant should be assigned one of the following categories: 1) complete response, 2) partial response, 3) stable disease, 4) progressive disease, 5) early death from malignant disease, 6) early death from toxicity, 7) early death because of other cause, or 9) unknown (not assessable, insufficient data). By arbitrary convention, category 9 usually designates the "unknown" status of any type of data in a clinical database.

Subjects who are removed from protocol prior to first restaging for reasons other than toxicity or disease progression may be replaced.

All conclusions should be based on all eligible participants. Subanalyses may then be performed on the basis of a subset of participants, excluding those for whom major protocol deviations have been identified (e.g., early discontinuation of treatment, major protocol violations, etc.). However, these subanalyses may not serve as the basis for drawing conclusions concerning treatment efficacy, and the reasons for excluding participants from the analysis should be clearly reported. The 90% confidence intervals should also be provided.

